30.0 Drugs or Devices

N/A

ATTACHMENTS:

- a. Interview battery
- b. Patient Consent
- c. ED Provider Consent
- d. ED Provider draft survey
- e. Follow-up provider (PCP & pharmacist) draft survey
- f. Safety Protocol
- g. MedSheet (health literacy format)
- h. Medication Diary
- i. Sample Text Messages
- j. DSMB Protocol
- k. Appointment Reminder Card
- l. Mini Mental Status Exam supplements

Statistical Analysis Plan

EHR-Based Medication Complete Communication Strategy to Promote Safe Opioid Use

NCT02431793

Document Date: June 7, 2019

Analysis Plan – Main Manuscript

Descriptive statistics were calculated for all socio-demographic, ED visit, and opioid prescription characteristics. Chi-square, one-way Analysis of Variance (ANOVA), and Wilcoxon rank-sum tests were used, as appropriate, to test for balanced randomization. An inter-cluster correlation assessment was conducted to assess the degree of independence among individuals in the same cluster. We used generalized linear mixed models on all outcomes adjusting for physician clustering. Models were run for dichotomous outcomes (safe demonstrated dosing, safe actual dosing; adjusted odds ratios [ORs] reported) and for continuous composite knowledge score (adjusted mean differences reported). Examination for possible associations between patient characteristics and outcome variables revealed significant was conducted, and all models controlled for covariates that related to the outcome. To isolate the effect of the SMS texting portion of the intervention from the EMC² EHR embedded tools a generalized linear mixed model was conducted utilizing two dummy variables (“emc2” for patients in both intervention arms, “text” for patients in EMC² +SMS arm) rather than the study arms on the primary and secondary outcomes as well as the individual knowledge or behavior questions linked to each text message. Significance for all analyses was set at $p < 0.025$ to adjust for multiple testing.

All analyses were first conducted using an intent-to-treat approach. Subsequently, because some patients did not receive one or more pieces of the intervention, the primary outcome was analyzed per-protocol, where the same methodology described previously was used but applied only to patients who successfully received all patient-facing pieces of the intervention. Patients in the EMC² arm were included in the per-protocol analysis if they received the MedSheet and the patient-centered TWS prescription wording on their bottle. Those in the EMC² +SMS arm were included in the per-protocol analysis if they received the MedSheet, TWS prescription wording on bottle, successfully enrolled in SMS texting, and received all seven text messages.

The planned enrollment target was for 816 patients to complete the 1-2 week follow-up interval, which would have provided 80% power to detect a difference of 11.8% (from pilot data) between each of the intervention arms and the usual care arm for the primary outcome of any error on the demonstrated dosing task. All analyses were performed using SAS 9.4 (SAS Institute Inc, Cary, NC).

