Patients with ED physicians randomized to the EMC² +SMS Text reminder arm will receive the above-described 5 components of the EMC² intervention, and also will receive daily text reminders for one week (7 messages) following the new prescription for an opioid pain reliever (only consented patients). The premise for the 1-week timeframe is to help patients remember precautions regarding safe use during the time they are taking the medication (average ED Rx for opioids is from pilot data is 18 tabs). Furthermore, SMS text reminders that would continue indefinitely are at risk for either being ignored, irritating patients, and/or adding an unnecessary expense to patients (i.e., patient does not have an unlimited texting plan, further challenging sustainability). Messages sent early in the week will focus on topics such as safe storage and use; those sent near the end of the week will focus on topics such as disposal and pill sharing. We will schedule EMC² text messages to arrive mid-day (12:00pm to 5:00pm), based on patient preference. (See appendix for sample text messages)

9.3 Procedures to monitor safety and minimize risk.

As a part of all of the time points of follow-up, the RAs will have a checklist of potentially dangerous behaviors related to opioids and if these items are noted in the course of data collection the RAs have a set protocol to follow. (see safety protocol attached)

9.4 The drug hydrocodone-acetaminophen is the topic of the research; however it is not being used in the research—the intervention is focused on education about this medication and the study will not change the drug, dose, frequency, quantity or refills that the ED physician selects in the course of their normal clinical care.

Sources of Materials:

Electronic Health Record (EHR): Patient information and outcomes will be extracted from the EHR (demographics, ED return visits and re-admissions). Re-admissions and re-visits to the hospital and ED data will be abstracted from medical records for all patients enrolled into the study, as well as all patients prescribed an opioid during the recruitment period of 18-months.

EHR-Based Medication Complete Communication (EMC²) Strategy to Promote Safe Opioid Use: A Physician Randomized Trial

Illinois Prescription Monitoring Program (ILPMP): We will obtain data from the ILPMP on medication fill date, subsequent refills of the prescribed opioid, and new prescriptions for other controlled substances.

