11.0 Data and Specimen Management

- 11.1 AIM 1 Analysis Plan. The proposed trial uses a cluster-randomized design where the prescribing physician is the unit of randomization. We will randomize approximately 150 physicians (50 attending physicians, 100 EM resident physicians and mid-level providers) to three intervention arms (usual care, EMC², and EMC² + SMS text reminders). The estimate of 150 includes a base of 100 providers with an estimate of approximately 50 new providers over the course of the 18 months of recruitment (e.g. 15 new residents in 2015, 15 new residents in 2016 and new attending hires). At any given time, we estimate that 100 providers will be actively involved in the study, resulting in approximately 33-34 physicians per arm. Physicians will be stratified by provider role (i.e., attending vs. resident) and randomly assigned to one of the three arms with an equal number assigned to each. We will accrue approximately 12 patients per physician; we conservatively anticipate at least 54% retention for the phone call follow-up 7-14 days post prescription. These estimates will result in 1500 participants recruited with an anticipated

EHR-Based Medication Complete Communication (EMC²) Strategy to Promote Safe Opioid Use: A Physician Randomized Trial

minimum of 816 patients at in-person follow-up (272 per arm, 8 per physician) available for primary data analysis.

To ensure adequate balance across the 3 arms, potential confounders including socio-demographic characteristics, comorbidities, regimen complexity (i.e., # of medications, total pills taken daily), health literacy level, and history of opioid use will be compared using one-way ANOVA models and χ^2 tests, as appropriate. Covariates with significant differences (p -value $< .05$) across treatment groups will be included in the generalized linear mixed models (GLMMs) to adjust for the group differences as described below. We note that detected differences may be physician-specific, so if we observe differences across the treatment arms, we will explore whether the difference might be attributable to individual physicians.

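### The baseline balance tests ignore that physicians were randomised, so they flag imbalance in prescriber-driven characteristics more often than the nominal rate

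*SAP*

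**What the plan says.** Protocol 11.1 names the design: "The proposed trial uses a cluster-randomized design where the prescribing physician is the unit of randomization". The SAP (Analysis Plan – Main Manuscript) names the tests by which balance between the arms is judged: "Chi-square, one-way Analysis of Variance (ANOVA), and Wilcoxon rank-sum tests were used, as appropriate, to test for balanced randomization". The variables it describes at baseline are not limited to patient traits, and they include what the prescriber writes: "Descriptive statistics were calculated for all socio-demographic, ED visit, and opioid prescription characteristics".

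No clustering allowance is attached to these tests. Clustering enters in a separate assessment of inter-cluster correlation and in the outcome models: "We used generalized linear mixed models on all outcomes adjusting for physician clustering". On the threshold, the SAP says: "Significance for all analyses was set at $p < 0.025$ to adjust for multiple testing".

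Protocol 11.1 also compares the arms with one-way ANOVA and chi-square tests, and it acts on the result. Covariates that differ at p<.05 "across treatment groups will be included in the generalized linear mixed models (GLMMs) to adjust for the group differences". It adds that a detected difference may belong to particular physicians and that this will be explored. The SAP does not repeat the p<.05 rule; it adjusts for covariates that are related to the outcome.

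On who determines the prescription, protocol 9.4 says that "the study will not change the drug, dose, frequency, quantity or refills that the ED physician selects".

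**The concern.** Chi-square, ANOVA and rank-sum tests assume independent patients. Here each physician contributes several patients, all in one arm. If a characteristic varies between physicians, the arm means vary by chance more than these tests allow, and the p-values are too small.

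Prescription characteristics are where this is most plausible, because the randomised physician chooses them. The protocol itself expects prescribers to differ, since section 9.2 stratifies on historical opioid volume. The ICC of 0.001 in section 11.2 offers no reassurance here: its rationale concerns patient outcomes.

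What is at stake is the reading of the baseline comparison. Physicians help to identify patients after allocation (sections 3.1 and 22.3). Physicians in the intervention arms are trained in how to prescribe with the new instructions (section 9.2). A falsely small p-value could be taken for differential recruitment, or for an effect of the intervention on prescribing, which section 9.4 says the study does not have. Under the protocol's rule it could also change the covariates in the primary model.

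A smaller wording point: the rank-sum test in the SAP is a two-sample test, the trial has three arms, and the SAP does not say which arms are compared.

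**Working it through.** **The plan's own figures.** The documents state no error rate for the balance tests, so there is none to reproduce. The cluster counts can be checked: 3 arms × 34 physicians × 8 patients = 816, as stated in protocol 11.1.

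**Inputs**

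- Patients per physician, m (protocol 4.1 and 11.1): 1500/150 = 10 over all physicians; 1500/100 = 15 if only the 100 active at one time are counted; about 12 as stated; 8 at the 7-14 day call. The documents do not say whether the tests use enrolled or followed-up patients.
- Nominal level: 0.05 (protocol 11.1) and 0.025 (SAP).
- ICC, ρ: 0.001 is the only documented value and was set for outcomes. Values of 0.02 to 0.20 are assumptions.

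**Formula.** With equal clusters, the variance of an arm mean is inflated by DE = 1 + (m − 1)ρ. A three-arm test has 2 degrees of freedom, and a chi-square variable with 2 df exceeds x with probability exp(−x/2). The true rejection rate of the unadjusted test, with no real imbalance, is therefore α^(1/DE).

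Example, m = 10 and ρ = 0.10: DE = 1 + 9 × 0.10 = 1.9. Then 0.05^(1/1.9) = 20.7% and 0.025^(1/1.9) = 14.3%.

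**True rate at nominal 5% (nominal 2.5% in brackets)**

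| ICC | m = 8 | m = 10 | m = 15 |
|---|---|---|---|
| 0.001 | 5.1% (2.6%) | 5.1% (2.6%) | 5.2% (2.6%) |
| 0.02 | 7.2% (3.9%) | 7.9% (4.4%) | 9.6% (5.6%) |
| 0.05 | 10.9% (6.5%) | 12.7% (7.9%) | 17.2% (11.4%) |
| 0.10 | 17.2% (11.4%) | 20.7% (14.3%) | 28.7% (21.5%) |
| 0.20 | 28.7% (21.5%) | 34.3% (26.8%) | 45.5% (37.9%) |

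**Check by simulation.** For a binary variable (prevalence 0.3) tested by chi-square, with 50 physicians per arm and 10 patients each, the rejection rates at nominal 5% were 12.3%, 19.8% and 34.4% at ICC 0.05, 0.10 and 0.20. At nominal 2.5% they were 7.1%, 13.6% and 26.5%. With 34 physicians per arm and 8 patients each, they were 10.9%, 16.4% and 29.7% at nominal 5%. Unequal cluster sizes (assumed coefficient of variation 0.6, mean 8) raised these to 14.0%, 21.3% and 36.7%.

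**Stratification.** Section 9.2 stratifies physicians by role and historical opioid volume. If the strata explain a share s of the between-physician variance, the factor becomes approximately mρ(1 − s) + (1 − ρ). Taking s = 0.5 as an assumption, with m = 10 and ρ = 0.10: 10 × 0.10 × 0.5 + 0.90 = 1.4, and 0.05^(1/1.4) = 11.8%, compared with 20.7% without stratification.

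**After the fix.** ANOVA on physician means rejected in 4.3% to 5.6% of simulations at nominal 5%, and in 2.1% to 3.2% at nominal 2.5%, for every ICC tried from 0 to 0.2.

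**The case against.** The strongest reply is that little depends on these tests, and that the plan already has safeguards.

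- *The physician check in protocol 11.1 and the SAP's inter-cluster correlation assessment.* Both make a misreading less likely. Neither corrects the p-values, and the first comes into play only after a flag.
- *The overlap between inflated tests and the covariate rule is small.* This stands. The variables named in protocol 11.1 are mostly patient traits (demographics, comorbidities, literacy, opioid history), and section 11.2 describes patients as reaching physicians at random. At most the daily pill count could partly reflect the prescriber, although the list is not exhaustive. Prescription characteristics are named only in the SAP, which does not select covariates by imbalance.
- *The large ICCs are assumed.* This also stands. Stratification, and eligibility restricted to pill-form hydrocodone-acetaminophen (section 3.2), could both reduce prescribing variation between physicians.
- *The rank-sum test may be meant pairwise.* That is possible, since the planned contrasts with usual care are pairwise and the SAP says the tests were used as appropriate. It remains a point of wording.

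A reader might also infer that false flags could conceal a real recruitment difference. They could not: a test that rejects too often flags more variables, not fewer. The risk is of imitating a difference.

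**Conclusion.** The tests as written do not match the randomised unit. For any variable with positive within-physician correlation, they flag imbalance more often than the nominal rate. At ICC 0.05 to 0.20 and 10 patients per physician, the true rate is about 2.5 to 7 times nominal 5% (12.7/5 to 34.3/5) and about 3 to 11 times nominal 2.5% (7.9/2.5 to 26.8/2.5). These multiples rest on assumed ICCs, equal cluster sizes and no gain from stratification. Unequal sizes raise them; informative strata lower them. At the only documented ICC the excess is 0.1 to 0.2 percentage points.

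Two stronger readings are tempting and not supported. The first is that the tests are known to be badly inflated in this trial: no document gives an ICC for a prescription characteristic, so the size is conditional. The second is that the treatment estimate is compromised: under the SAP, covariates are chosen by relation to the outcome and the outcome models account for physician. The effect there is mainly on the baseline table and the verdict on balance. Only the p<.05 rule in protocol 11.1 gives a false flag a route into the primary model, and that route is narrow.

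The correction is still worth making, because the analysis is wrong as written and the repair is cheap.

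**What to change.** 1. In the SAP, take one of two routes for the baseline table. Either present characteristics by arm without p-values, which is simplest. Or test each with three-level arm as a fixed effect and physician as a random effect. For skewed variables, use a physician-level test, or permute physicians' arm labels within the randomisation strata, in place of the rank-sum test.
2. Report the ICC of the prescription characteristics, so that a reader can judge how much clustering there was.
3. In protocol 11.1, stop using unclustered p<.05 balance tests to select covariates for the GLMM, and state one covariate rule that the protocol and SAP share.

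The cost is a few lines of wording and a re-run of the baseline table on existing data. Fewer variables will be flagged. No new data are needed.

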Demonstrated safe use by not exceeding the maximum dose is the primary outcome of interest for Aim 1 (H_3), with higher reported rates of provider counseling and greater understanding of risks relevant to hypotheses of secondary interest for Aim 1 (H_1, H_2). We will use GLMMs for analyses of the data, specifying the logit link function for the binary outcomes using xtmixed in Stata (v.12.1). The 3-category treatment group variable will be the independent variable of primary interest and modeled as a fixed effect with the usual care group specified as the reference. We will also include fixed effects for any potential confounding covariates noted in the descriptive studies that were not accounted for in randomization. Random effects will be included for each physician to account for intra-physician correlation among participants. For all GLMM analyses we will report point estimates and corresponding 95% confidence intervals. We will examine and report the extent to which the random effects suggest correlation of outcomes within physicians.

Measures taken to minimize bias. For the randomization scheme of this study, physician is the unit of randomization rather than patient. With healthcare interventions and quality improvement projects, such as the one proposed herein, there are no other ways to evaluate an automated EHR process than to “turn them on.” This is why the randomization will occur at the physician level rather than the patient level. This process will result in trickle down of aspects of the EMC² intervention (but not SMS texting) to patients seen by the consented provider, but not enrolled in the study for follow-up purposes (e.g., on overnight shifts).

Level of significance to be used. We will use a two-sided 5% significance test

Stopping rules. We will stop enrollment once we have reached the 1500 patient enrolled maximum.

EHR-Based Medication Complete Communication (EMC²) Strategy to Promote Safe Opioid Use: A Physician Randomized Trial

Procedures for reporting deviations from the original plan. Any deviations involving human subjects will be submitted to the IRB for review before being implemented.

Selection of subjects for inclusion in the analysis. All subjects with complete information (e.g., at least 80% completion of interview instrument) will be used in the analysis.

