EHR-Based Medication Complete Communication (EMC²) Strategy to Promote Safe Opioid Use: A Physician Randomized Trial

estimates to different proficiency levels that could arise from learning by doing.

To achieve Aim 3, [name], at UIC, will help in analyzing time and resource use related to the intervention. Any data that he would receive would be anonymous and would not contain any patient PHI. Instead, the data would involve counts of hours spent, and materials used, in creating and implementing the intervention.

11.2 Rationale for choice of sample size, power considerations. The sample size for this study was based on pairwise comparisons between the two intervention arms compared to usual care (i.e., usual care vs. EMC² and usual care vs. EMC² + SMS). This calculation was based on the primary outcome of demonstrating safe use by not exceeding the maximum recommended dose at the 7-14 day phone follow-up interview.

Conservatively estimating 54% retention rate for 7-14 day follow-up call, we will have 82% to detect a difference of 11.8% between each intervention and the usual care arm assuming a Type I error of 2.5% to account for the two comparisons. An intraclass correlation coefficient (ICC) of 0.001 was used because we do not expect patient outcomes to be influenced by the clustering of physicians due to patients being randomly assigned a physician upon ED entrance and physicians typically working a random assortment of shifts.

With the sample size set by the primary outcome of demonstrated safe use by not exceeding the maximum dose, we also show detectable effects for the secondary outcomes in Table 3, assuming at least 80% power, a Type 1 error rate of 2.5%, an ICC of 0.001, and usual care estimates from prior studies.

11.3 Data Safeguarding Procedures. Any information that could allow identification of individual patients, including the master list, will be kept strictly confidential. In order to preserve participants' confidentiality rights, research subjects will be assigned study ID numbers that will be used to identify all the information collected. A master study tracking database will contain information linking participants to their study ID numbers. This database will be on RedCap and is both encrypted and password protected and only accessible by approved study personnel at Northwestern. Grant file access permissions will only be given to specific approved research personnel, as designated by the PI.

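### The SAP presents p<0.025 on all analyses as a multiplicity adjustment, but that level accounts only for two contrasts within one outcome, and the protocol's 95% intervals do not match it

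*SAP*

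**What the plan says.** **SAP, Analysis Plan – Main Manuscript.** "Significance for all analyses was set at $p < 0.025$ to adjust for multiple testing". No other multiplicity procedure is given. The SAP names three modelled outcomes: safe demonstrated dosing, safe actual dosing and a knowledge score. It then describes a second model in which two indicators, 'emc2' (both intervention arms) and 'text' (EMC²+SMS only), replace the study arms. That model is fitted "on the primary and secondary outcomes as well as the individual knowledge or behavior questions linked to each text message". These tests are neither ordered nor labelled exploratory.

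**Protocol section 11.2.** "The sample size for this study was based on pairwise comparisons between the two intervention arms compared to usual care". The level is set "assuming a Type I error of 2.5% to account for the two comparisons". The same 2.5% is carried to the secondary outcomes, each with planned power of at least 80%, and is not divided among them.

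**Protocol section 11.1.** On the level: "We will use a two-sided 5% significance test". On reporting: "For all GLMM analyses we will report point estimates and corresponding 95% confidence intervals". The SAP gives no interval level.

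**Protocol section 9.2.** The SMS arm receives seven daily messages. The number of interview questions linked to them is not stated.

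**The concern.** A correction for two comparisons is described as if it adjusted every analysis. Aim 1 asks about EMC² with and without text reminders. Whether the reminders add anything to EMC² rests on the 'text' term and the message-linked questions, which the two-comparison reasoning does not reach. Under the SAP's wording, one such result at p<0.025 could be reported as having survived a multiplicity adjustment.

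The second problem concerns the primary contrasts. Readers commonly judge significance by whether the interval excludes no effect. If the intervals are at 95% and the test is at 0.025, the two can disagree, and a reader who relies on the intervals loses the error control that 0.025 was chosen to give.

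**Working it through.** **Inputs.** Two-sided 5% overall and 95% intervals (protocol 11.1); 2.5% per contrast, 11.8 points, 82% power, ICC 0.001 (protocol 11.2); 272 per arm, 8 per physician (protocol 11.1); 80% power for 11.8 points (SAP). The design effect is 1 + (8 − 1) × 0.001 = 1.007, so clustering is ignored below. Test statistics are taken as normal, arms as equal, and error rates are computed with no true effects. Critical values are 2.241 for two-sided 0.025 and 1.960 for two-sided 0.05.

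**1. The plan's own figure.** 0.05 / 2 = 0.025. Two contrasts sharing a usual-care arm correlate at 0.5, and the chance that either exceeds 2.241 is about 4.6%. The 2.5% does its job within one outcome.

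**2. Adding 'text'.** With both indicators in the model, 'emc2' is EMC² versus usual care (already counted) and 'text' is EMC²+SMS versus EMC². Only 'text' is new. Three contrasts at 0.025 have a bound of 3 × 0.025 = 7.5%; simulation for three equal arms gives 6.4%.

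**3. 'Text' on the linked questions alone.** For k uncorrelated questions the rate is 1 − 0.975^k; for k = 7 this is 16.2%. Seven assumes one question per message. With a common correlation between questions:

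| Questions | corr. 0 | corr. 0.6 | corr. 0.9 |
|---|---|---|---|
| 4 | 9.6% | 7.7% | about 5% |
| 7 | 16.2% | 11.3% | 6.1% |
| 10 | 22.4% | 14.1% | about 7% |

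**4. Across outcomes.** Three outcomes with two usual-care contrasts each give 13.3% at correlation 0 between outcomes, 11.2% at 0.6 and 8.0% at 0.9. The correlations are assumed.

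**5. Intervals against the test.** A 95% interval excludes no effect at |z| > 1.960, while the test needs |z| > 2.241. The ratio 2.241 / 1.960 = 1.14, so a matching 97.5% interval is 14% wider. Reading both primary contrasts from 95% intervals gives a family-wise error of about 9%.

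For the chance of disagreement at the planned effect:
- At 82% power the expected z is 2.241 + 0.915 = 3.157. P(1.960 < z < 2.241) = Φ(−0.915) − Φ(−1.197) = 6.4%.
- At 80% power the expected z is 2.241 + 0.842 = 3.083, and the chance is 6.9%.

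In planning units, the standard error at 82% power is 11.8 / 3.157 = 3.74 points. Half-widths are 1.960 × 3.74 = 7.3 and 2.241 × 3.74 = 8.4 points. At 80% power they are 7.5 and 8.6. These are risk-difference figures; the SAP reports odds ratios, so they show scale only.

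**The case against.** The strongest reply is that no primary claim is exposed. Hypotheses H1 to H3 are all comparisons with usual care, and within one outcome those two contrasts are held at about 4.6%. That stands.

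A second reply is that the indicator model also contains exactly two terms. Their estimates correlate at −0.5, so that pair alone is held at about 4.6% too. That is correct. The 6.4% arises only when all three contrasts on an outcome are taken together, and the documents define no such family. This reply does not reach the linked questions, each of which has its own model.

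Third, the SAP asserts no family-wise rate, and 0.025 is stricter than leaving secondary tests at 0.05. This is fair. The fault is that the stated reason is attached to all analyses without saying what it covers.

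Fourth, 95% intervals beside a stricter threshold are a presentation choice and do not change which results are declared significant. This is also true, and the mismatch runs across two documents because the SAP names no interval level. It still matters to anyone who reads significance from the intervals. A one-sided reading of 0.025 would match a 95% interval, but it would then be no multiplicity adjustment, and the protocol says two-sided.

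**Conclusion.** The point holds as a matter of scope and reporting. The 0.025 level is a sound correction for two usual-care contrasts within an outcome. It does not control error across all three arm contrasts, across the message-linked questions, or across outcomes, and the SAP's wording does not say so. The 6.4% for three contrasts needs only equal arms and negligible clustering. The question-level figure depends on an unstated number of questions and their correlation: from about 5% (four questions, correlation 0.9) to 22.4% (ten, uncorrelated). The interval mismatch follows directly from the two stated levels.

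A reader might infer three stronger things that the documents do not support:
- That the primary analysis has inflated error. It does not.
- That the protocol's 5% contradicts 2.5%. The natural reading is 5% overall, split over two comparisons.
- That secondary outcomes are unadjusted and should carry no significance claims. Protocol 11.2 plans them at 2.5% with at least 80% power, so they are adjusted for two contrasts within each outcome, though not for the number of outcomes.

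**What to change.** Replace the SAP's significance sentence with wording such as:

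> The overall two-sided 5% type I error rate applies to two intent-to-treat comparisons on the primary outcome: EMC² versus usual care and EMC²+SMS versus usual care. Each is tested at p<0.025 and reported as an adjusted odds ratio with a 97.5% confidence interval. For each secondary outcome the same two comparisons are tested at p<0.025; this accounts for two comparisons within that outcome and not for the number of outcomes. The text contrast and the questions linked to text messages are supplementary, and error is not controlled across that set.

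Amend the 95% interval statement in protocol section 11.1 to agree for the primary contrasts. The SAP is dated June 2019 and written in the past tense, so the report should say when this wording was adopted.

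**Cost.** A few sentences. Data, models, sample size and the primary threshold do not change. Primary intervals become about 14% wider on the analysis (log-odds) scale, and 'text' and question-level results can no longer be presented as multiplicity-controlled.

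Testing all three contrasts at 0.05 / 3 = 0.0167 is not needed and would cost power. With 272 / 1.007 = 270 per arm and an assumed 20% versus 31.8%, power falls from 81.5% to 77.1%; with 12% versus 23.8%, from 91.2% to 88.4%; with 30% versus 41.8%, from 73.3% to 68.0%. The documents do not give the usual-care rate.
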